7 STATISTICAL METHODOLOGY FOR SAFETY

Patients are evaluable for general safety if they received any study treatment.

7.1 Toxicity and adverse events

All the adverse events will be coded using the Medical Dictionary for Regulatory Activities (MedDRA).

The toxicity evaluation will be coded with the National Cancer Institute-Common Terminology Criteria for Adverse Events (NCI-CTCAE), version 4.

As far as all the toxicities are concerned, the NCI-CTCAE grade will be used wherever an NCI-CTCAE grading exists. Otherwise, the severity will be noted. As a convention, the term «Grade» will always be used. Toxicities will be described according to the worst NCI-CTCAE grade or, for toxicities which do not form the subject of NCI-CTCAE classification, according to the worst severity. For “Worst per cycle” calculation purpose, onset and end cycle of each event will be derived.

Summary of overall adverse events will be done by body system and preferred term, by severity (worst toxicity grade) and by relationship to the study drug. Events with unknown relationship will be considered as related events for reporting purposes.

A frequency table will be made for the AEs leading to cycle delay, dose reduction, skipped dose, or withdrawal of study medication. Adverse events with outcome of death will also be presented by relationship to the study drug.

All events entered in Adverse Event form with the onset date before the first drug administration, will be reported as Signs and symptoms. Only those events with start date after/equal the first infusion date will be included in AE tables in Safety section (except those including evolution from baseline).

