- (11) Diagnosis and/or re-biopsy specimens are required for central pathological review and prior to each futility analysis. An incisional or excisional biopsy is preferred but a core-needle biopsy can be considered when excisional biopsy is not possible. Archived tissue samples of representative tumors: a formalin-fixed paraffin-embedded (FFPE) tissue block (preferred) or freshly-cut unstained tumor slides. Collect 10 mL blood at the same time as the first PK sample on Day 1: one whole blood sample for germline DNA extraction (6 mL) and another blood sample (4 mL) to obtain plasma. A separate instruction manual for sites will be provided.

(12) Clinical assessment of the patient's signs and symptoms (if any and including nurses' assessment and patient-reported issues) should continue on an ongoing basis throughout the study and be reported at least every cycle as AEs graded according to NCI-CTCAE v.4: between IC and Day 0, AEs are considered baseline and non-treatment emergent.

**Hematology:** Differential white blood cells (WBC), hemoglobin, hematocrit and platelets.

**Biochemistry-A:** AST, ALT, total bilirubin (direct bilirubin if total bilirubin  $> 1.5 \times$  ULN), ALP, creatinine, calculated creatinine clearance (Cockcroft-Gault formula), glucose, serum electrolytes ( $\text{Na}^+$ ,  $\text{K}^+$ ,  $\text{Mg}^{++}$ ,  $\text{Ca}^{++}$ ) and CPK (CPK-MB fraction should be measured if CPK is abnormally high).

**Biochemistry-B:** Uric acid, LDH, total proteins, albumin and C-reactive protein.

**Coagulation tests:** PT, PTT and INR.

ABP, arterial blood pressure; AE, adverse event; ALT, alanine aminotransferase; ALP, alkaline phosphatase; AST, aspartate aminotransferase; BM, bone marrow; CPK, creatine phosphokinase; CPK-MB, creatine phosphokinase-isoenzyme MB; ECG, electrocardiogram; ECHO, echocardiogram; ECOG, Eastern Cooperative Oncology Group; EOT, end of treatment; HR, heart rate; IC, Informed Consent; INR, international normalized ratio; LDH, lactic dehydrogenase; LVEF, left ventricular ejection fraction; MUGA, multiple-gated acquisition scan; NCI-CTCAE, National Cancer Institute Common Terminology Criteria for Adverse Events; PD, progressive disease; PS, performance status; PT, prothrombin time; PTT, partial thromboplastin time; SAE, serious adverse event; TTP, time to progression; ULN, upper limit of normality; WBC, white blood cells; wk, week; WOCBP, woman of childbearing potential.

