## **8.5 ADVERSE EVENTS DEFINITIONS**

### **8.5.1 Adverse Event (AE)**

An AE is any untoward medical occurrence in a patient or clinical investigation patient administered a pharmaceutical product which does not necessarily have a causal relationship with this treatment.

An AE can therefore be any unfavorable and unintended sign, (e.g., an abnormal laboratory finding), or a disease temporally associated with the use of a medicinal product, whether or not considered related to the medicinal product.

Illnesses with onset during the study or exacerbations of pre-existing illnesses, including but not limited to clinically significant changes in physical examination findings and abnormal objective test findings (e.g., X-ray, ECG) should be recorded. The criteria for determining whether an abnormal objective test finding should be reported as an AE are as follows:

- The test result is associated with clinically significant symptoms, and/or
- The test result leads to a change in the study dosing or discontinuation from the clinical trial, significant additional concomitant drug treatment or other therapy, and/or
- The test result leads to any of the outcomes included in the definition of a SAE (see definition below), and/or
- The test result is considered to be clinically relevant by the Investigator.

For the purposes of this protocol, disease progression, worsening of the underlying disease or appearance of new tumor lesions, or any sign or symptom clearly related with this circumstance is NOT an AE.

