7.2 Clinical laboratory evaluation

Laboratory results will be classified according to the NCI-CTCAE version 4. All laboratory visits reported as “End of treatment” visit will be mapped to the last cycle visit.

For hematology values: absolute neutrophil count, lymphocyte count, WBC count, platelet count and hemoglobin worst grade per patient and per cycle will be displayed.

Time and duration of anemia, neutropenia and thrombocytopenia in cycles with grade 3-4 abnormality will be tabulated.

Overall cross tabulation will be presented for the worst grade during treatment versus the baseline toxicity grading of anemia, lymphopenia, leukopenia, neutropenia and thrombocytopenia.

The worst grade per patient during treatment and per cycle will be also calculated for the biochemical tests: ALT, AST, Total bilirubin, AP, CPK, creatinine, calcium, potassium, sodium, glucose and albumin.

Time and duration of AST, ALT and CPK increases in cycles with grade 3-4 abnormality will be tabulated.

Overall cross tabulation will be presented for the worst grade during treatment versus the baseline toxicity grading of AST, ALT and CPK increase.

7.3 Vital signs, physical examination, left ventricular ejection fraction (LVEF) and electrocardiogram findings

Tabulation will be made summarizing the performance status, body weight, LVEF and electrocardiogram abnormalities at baseline and during the treatment for each patient.

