12.2 Adverse Events (AEs)

12.2.1 Display of adverse events

Table 12.2.1.1 Summary of adverse events.

	N (%)
Patients with at least one AE regardless relationship	X (X.X)
Any treatment-related AE	
Any grade 3/4 AE	
Any grade 3/4 treatment-related AE	
Any SAE in DB	
Any treatment-related SAE	
Any grade 3/4 SAE	
Any grade 3/4 treatment-related SAE	
AEs leading to death	
AEs treatment-related leading to death	
AEs leading to dose delay	
AEs leading to dose reduction	
AEs leading to treatment discontinuation	
AEs treatment-related leading to treatment discontinuation	

Table 12.2.1.2 Evolution of lymphoma-related AEs at baseline

		Worst grade per patient						Total		
		0		1		...		N	%	
		N	%	N	%	N	%			
Baseline	Fatigue	Grade 0	X	X.X	X	X.X	X	X.X	X	X.X
		Grade 1								
									
	Bone Pain	Grade 0								
		Grade 1								
									
	Myopathy	Grade 0								
		Grade 1								
									

Table 12.2.1.3 Treatment-related* adverse events. Worst grade by patient

	Preferred Term	Grade 1		...	Grade 4		All**	
		N	%	...	N	%	N	%
SOC	Anemia NOS	X	X.X		X	X.X	X	X.X
Blood and lymphatic system disorders	...							
Cardiac disorders	Arrhythmia NOS							
	...							

(* or Unknown relationship (***) Any grade

Table 12.2.1.4 Treatment-related* adverse events. Worst grade by cycle

	Preferred Term	Grade 1		...	Grade 4		All**	
		N	%	...	N	%	N	%
SOC	Preferred Term	N	%	...	N	%	N	%
Blood and lymphatic system disorders	Anemia NOS	X	X.X		X	X.X	X	X.X
	...							
Cardiac disorders	Arrhythmia NOS							
	...							

(* or Unknown relationship (** Any grade

Table 12.2.1.5 Adverse Events regardless of relationship. Worst grade by patient

	Preferred Term	Grade 1		...	Grade 4		All*	
		N	%	...	N	%	N	%
SOC	Preferred Term	N	%	...	N	%	N	%
Blood and lymphatic system disorders	Anemia NOS	X	X.X		X	X.X	X	X.X
	...							
Cardiac disorders	Arrhythmia NOS							
	...							

(* Any grade

Table 12.2.1.6 Adverse Events regardless of relationship. Worst grade by cycle

	Preferred Term	Grade 1		...	Grade 4		All*	
		N	%	...	N	%	N	%
SOC	Preferred Term	N	%	...	N	%	N	%
Blood and lymphatic system disorders	Anemia NOS	X	X.X		X	X.X	X	X.X
	...							
Cardiac disorders	Arrhythmia NOS							
	...							

(* Any grade

Listing 12.2.1.7 Treatment-related* grade 3-4 adverse events. Worst grade by patient

Patient id.	SOC Name	Preferred term	Grade

(* or Unknown relationship

Listing 12.2.1.8 Treatment-related* grade 3-4 adverse events. Worst grade by cycle

Patient id.	Cycle	SOC Name	Preferred term	Grade

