12.4.4 Laboratory values over time

In this section, grades 3-4 hematological and liver enzyme abnormalities will be displayed according to the cycle in which they occurred.

Table 12.4.4.1 Evolution of hematological abnormalities from baseline, worst case per patient.

			Worst grade per patient					Total	
			0	1	...				
Baseline	Neutropenia	Grade 0							
		Grade 1							
								
	Thrombocytopenia	Grade 0							
		Grade 1							
								
	Grade 0							
		Grade 1							
								

Table 12.4.4.2 Evolution of transaminases abnormalities from BL, worst case per patient.

			Worst grade per patient						Total	
			0		1		...		N	%
			N	%	N	%	N	%	N	%
Baseline	AST increase	X	X.X	X	X.X			X	X.X	
		Grade 1								
									
	ALT increase	Grade 0								
		Grade 1								
									
	Grade 0								
		Grade 1								
									

Table 12.4.4.3 Grade 3-4 laboratory abnormalities in the first cycle and in all other cycles

Laboratory abnormalities						
	Cycle 1			Cycle>1		
	No. of cycles evaluated	No. of cycles grade 3-4	%	No. of cycles evaluated	No. of cycles grade 3-4	%
Thrombocytopenia	X	X	X.X	X	X	X.X
Neutropenia						
ALP						
Total bilirubin						
AST						
ALT						
CPK						

Table 12.4.4.4 Hemtological time-course pattern

Laboratory abnormalities	Onset day grade 3-4	Days in grade 3-4	Day of recovery to grade 2			Days to recovery		
			<=28	29-35	>35	<=28	29-35	>35
Anemia	X (X-X)	X (X-X)	X (X.X%)	X (X.X%)	X (X.X%)	X (X.X%)	X (X.X%)	X (X.X%)
Neutropenia								
Thrombocytopenia								

Table 12.4.4.5 ALT/AST/CPK time-course pattern

Laboratory abnormalities	Onset day grade 3-4	Days in grade 3-4	Day of recovery to 2.5 x ULN			Days to recovery		
			<=28	29-35	>35	<=28	29-35	>35
ALT	X (X-X)	X (X-X)	X (X.X%)	X (X.X%)	X (X.X%)	X (X.X%)	X (X.X%)	X (X.X%)
AST								
CPK								

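### SAP 7.1 selects events for the AE tables by start date alone, so on-treatment worsening of a symptom already present before dosing can drop out of the AE and SAE frequency tables

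*SAP*

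**What the plan says.** SAP 7.1 gives two linked rules. Events with earlier onset are moved out of the AE tables: "All events entered in Adverse Event form with the onset date before the first drug administration, will be reported as Signs and symptoms". What remains is then defined by date: "Only those events with start date after/equal the first infusion date will be included in AE tables in Safety section". The second sentence goes on to an exception, so that the restriction governs what is "included in AE tables in Safety section (except those including evolution from baseline".

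The protocol takes a wider view of what an AE is. Among the things to be recorded under its AE definition, Protocol 8.5.1 lists "Illnesses with onset during the study or exacerbations of pre-existing illnesses". Footnote 12 of the schedule of assessments sets the status of pre-treatment events: "between IC and Day 0, AEs are considered baseline and non-treatment emergent". Neither document defines a treatment-emergent event as one that starts or worsens after first dose.

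The table shells with a baseline-to-worst layout are, for clinical events, "Table 12.2.1.2 Evolution of lymphoma-related AEs at baseline" (rows shown: fatigue, bone pain, myopathy) and, for laboratory values, Tables 12.4.4.1 and 12.4.4.2.

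**The concern.** In this trial, symptoms of disease, residual effects of earlier therapy and effects of the drug overlap. Protocol 1.1.1 describes fever and other constitutional symptoms as almost constant in AITL. Inclusion criterion 6 admits patients with residual non-hematological events up to grade 1, and exclusion 2j bars myopathy only above grade 2. In the earlier trial of the same schedule, the most common AEs included nausea, fatigue, myalgia and pyrexia (Protocol 1.3, SAP 1). So some patients can be expected to start plitidepsin with a symptom that the drug may then aggravate.

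A rule that looks only at the start date cannot tell a stable pre-existing symptom from one that becomes severe on treatment. Where it applies, it can only lower the tabulated toxicity. Safety is a secondary objective, and the trial has a single arm (Protocol 5.7 states that randomization is not applicable), so no control group would show the shortfall.

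**Working it through.** No alpha, power or rate is involved. The check is to trace which tables the rule reaches and what happens to one event.

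**Step 1. Which tables the exception covers.** I read *those* in the exception as tables, because the wording matches the shell titles.

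| Display | Baseline evolution shown? | Start-date rule applies? |
|---|---|---|
| 12.2.1.2 (lymphoma-related AEs) | Yes | No |
| 12.4.4.1, 12.4.4.2 (laboratory) | Yes | No |
| 12.2.1.1 (AE summary) | No | Yes |
| 12.2.1.3 to 12.2.1.6 (AEs by worst grade) | No | Yes |
| 12.3.1.1 to 12.3.1.4 (SAEs by worst grade) | No | Yes |

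**Step 2. Trace one event.** Take a patient with grade 1 nausea left over from prior therapy, which criterion 6 allows, that reaches grade 3 in Cycle 2.

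| How the site records it | Start date | AE frequency tables |
|---|---|---|
| Higher grade on the existing record | Before first infusion | Absent; the event is classed under signs and symptoms |
| New record at worsening | After first infusion | Included at grade 3 |

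Nausea is not a row in the Table 12.2.1.2 shell, and residual nausea from earlier chemotherapy does not fit its title. In the first case the exception therefore does not bring it back. The same holds if the worsening makes the event serious, because the SAE frequency tables have no separate entry rule.

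**Step 3. Which recording route the documents require.** Protocol 8.5.1 wants exacerbations recorded but does not say whether this means a new record with its own start date. SAP 7.1 derives the onset cycle and end cycle of each event, which describes how long an event lasts and not when it worsened. Neither document settles the route.

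**Step 4. Size.** For a given event type, let f be the share of patients with that on-treatment event whose worsening sits on a record with a pre-dose start date. Then

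tabulated rate = true rate × (1 − f).

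If every site opens a new record, f = 0 and nothing is lost. If f is above 0, the proportional loss equals f. The documents give no baseline symptom frequencies, no worsening frequencies and no CRF convention, so f could lie anywhere from 0 to 1 and I put no figure on it.

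**Step 5. What lies outside the problem.** Laboratory toxicity is graded from laboratory values and compared with baseline. SAP 7.2 says "Overall cross tabulation will be presented for the worst grade during treatment versus the baseline toxicity grading of AST, ALT and CPK increase", and the hematology counterpart is "Table 12.4.4.1 Evolution of hematological abnormalities from baseline, worst case per patient". SAP 8.1 takes the last assessment up to first dose for baseline data, including signs and symptoms. SAE Listing 12.3.1.5, the pharmacovigilance narratives and Listing 13.1.27 are not tables and fall outside the wording of the rule.

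**The case against.** The strongest reply is that this is a data-entry question that the CRF instructions, which are not in these documents, may already answer. There are signs in that direction. Protocol 8.5.1 treats an exacerbation as something to record. Footnote 12 of the schedule calls for signs and symptoms to be reported and graded at least every cycle. SAP 12.2.1 tabulates worst grade by cycle. Table 12.2.1.2 needs a pre-dose grade held apart from a later one. All this fits separate records at worsening, and it shows that the data for a worsening rule are likely to be within reach. It does not establish that a worsened event receives a new start date, and start date is the only thing SAP 7.1 tests.

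A second reply is that *those* in the exception could mean events that evolve from baseline. On that reading they would enter the AE tables and the gap would close. The match with the table titles makes this the less natural reading. Even so, a rule that decides the AE counts should not rest on an ambiguous pronoun.

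Third, a reader might infer that a severe on-treatment grade would appear in the baseline symptom tables, or that serious worsening would vanish from the report. The documents support neither. SAP 8.1 fixes baseline data at the last assessment up to first dose, and serious events can still appear in SAE listings and narratives. The exception also keeps worsening of fatigue and myopathy visible in Table 12.2.1.2. These points narrow the problem to the frequency tables. They do not remove it, since listings do not correct tabulated rates.

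**Conclusion.** The point holds as a conditional one. SAP 7.1 has no worsening criterion for the AE summary, grade and SAE frequency tables, and this sits badly with Protocol 8.5.1. On-treatment worsening of a pre-dose symptom to grade 3-4, serious or drug-related can be left out of those tables if it stays on its existing record.

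The conclusion rests on two assumptions: that the exception refers to tables, and that at least some sites update an existing record instead of opening a new one. The first is the natural reading; the second cannot be checked from the documents. It would be tempting to say that reported toxicity rates *are* biased downward, or to attach a percentage. The documents support neither statement: the loss ranges from nil upward and has no derivable size. The primary endpoint is untouched. It is still worth correcting, because the rule is explicit, any error runs only towards lower toxicity, and a replacement is cheap.

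**What to change.** In SAP 7.1, replace the start-date rule with a definition: a treatment-emergent AE is one that starts on or after first infusion, or was present before first infusion and increases in grade, or becomes serious or drug-related, on or after first infusion, within the AE collection window of Protocol 8.6.1. Apply it to all frequency tables in SAP 12.2 and 12.3.

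Add one line to the CRF completion instructions: for any event present at baseline, record the date and grade of each worsening.

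The cost is the SAP wording, one derived flag and the CRF line. The downside is that AE rates may be slightly less favourable.

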7.2 Clinical laboratory evaluation

Laboratory results will be classified according to the NCI-CTCAE version 4. All laboratory visits reported as “End of treatment” visit will be mapped to the last cycle visit.

For hematology values: absolute neutrophil count, lymphocyte count, WBC count, platelet count and hemoglobin worst grade per patient and per cycle will be displayed.

Time and duration of anemia, neutropenia and thrombocytopenia in cycles with grade 3-4 abnormality will be tabulated.

Overall cross tabulation will be presented for the worst grade during treatment versus the baseline toxicity grading of anemia, lymphopenia, leukopenia, neutropenia and thrombocytopenia.

The worst grade per patient during treatment and per cycle will be also calculated for the biochemical tests: ALT, AST, Total bilirubin, AP, CPK, creatinine, calcium, potassium, sodium, glucose and albumin.

Time and duration of AST, ALT and CPK increases in cycles with grade 3-4 abnormality will be tabulated.

Overall cross tabulation will be presented for the worst grade during treatment versus the baseline toxicity grading of AST, ALT and CPK increase.

7.3 Vital signs, physical examination, left ventricular ejection fraction (LVEF) and electrocardiogram findings

Tabulation will be made summarizing the performance status, body weight, LVEF and electrocardiogram abnormalities at baseline and during the treatment for each patient.

7.4 Deaths and other Serious Adverse Events

Deaths and other Serious Adverse Events will be tabulated.

8 OTHER ANALYSES

Non-continuous variables will be described in frequency tables using counts and percentages. Continuous variables will be described by median, mean, standard deviation, minimum and maximum.

8.1 Baseline and demographic data

Baseline data such as demographics, disease history, prior therapy, prior relevant history, signs and symptoms, electrocardiogram, LVEF, protein measurements, laboratory values and concomitant medication (ATC-WHO coded) will be described following standard tables detailed in Appendix I. When two or more assessments have been done for the same parameter, the last assessment before or on the first drug administration will be taken into account for the analysis.

8.2 Treatment administration

CRF cycles with a theoretical duration of 4 weeks will be used for this analysis.

Total cumulative dose, time on treatment, dose intensity and relative dose intensity, cycle delay, dose omissions, and dose reductions will be described following standard tables detailed in Appendix I.

Total cumulative dose, expressed in mg/m² is the sum of all the plitidepsin doses from the first cycle until last cycle including the dose received in last cycle.

Patients will be considered to be on-treatment for the duration of their treatment and 30 days following the last treatment dose. If the patient starts any new antitumor therapy outside this clinical trial or dies within 30 days of last treatment dose, the date of administration of this new therapy or the date of death will be considered the date of treatment discontinuation.

However, as a convention, for dose intensity calculation purposes, the duration of the last cycle is considered to be 28 days.

Intended dose intensity is the planned dose per cycle divided by the planned number of weeks by cycle (2.4mg/m²/wk for plitidepsin).

Absolute dose intensity is the actual cumulative dose divided by the number of weeks of treatment. Relative dose intensity (%) is the ratio of absolute dose intensity divided by the intended dose intensity.

The item «Infusion delayed: yes/no» in the case report form (CRF) will be used to calculate the delay (on day 1 infusion). For cycles considered as delayed by the investigator, the delay will be calculated as:

Delay: Date of current drug administration – Date of previous drug administration – 28.

The first infusion of the first cycle will be excluded from all cycle delay and cycle modification calculations.

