## 7.2 ADMINISTRATION OF STUDY MEDICATION

Plitidepsin will be administered intravenously as a 1-hour infusion (fixed rate) via central or peripheral venous catheter.

Patients will receive plitidepsin at a starting dose of 3.2 mg/m^2 on Day 1, 8 and 15 every four weeks (q4wk). A 1-day window is allowed for plitidepsin administration.

A cycle is defined as a four-week period.

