12.1.2 Cycle delays

12.1.2.1 Number of patients and cycles with dosing delay, any relationship

Listing 12.1.2.1.1 Delays

Patient id.	Cycle	Day	Previous cycle	Previous cycle start date	Delayed cycle	Delayed cycle start date	Dose Delay calculated. (days)	Reason for dose delay	Dose Delay Spec.
							X		

Table 12.1.2.1.2 Number of patients and cycles with dosing delay, any relationship

	N	%
No. of patients treated	X	X.X
No. of patients susceptible to have a dosing delay*		
No. of patients with any dose delay**		
No. of cycles administered		
No. of cycles susceptible to be delayed***		
No. of cycles with dosing delay****		
No. of patients with		
No cycles delayed		
1 cycle delayed		
2 cycles delayed		
≥ 3 cycles delayed		

(*) All patients with more than one cycle. (**) Denominator = Number of patients susceptible to have a dosing delay

(***) All cycles excluding first cycle. (****) Denominator= Number of cycles susceptible to be delayed

Table 12.1.2.1.3 Number of patients and cycles with dosing delay according to the relationship

	Treatment-related		Non-treatment-related	
	N	%	N	%
No. of patients with *	X	X.X		
1 cycle delayed				
2 cycles delayed				
≥ 3 cycles delayed				
No. of cycles with dosing delay**				

(*) Denominator = Number of patients susceptible to have a dosing delay (**) Denominator= Number of cycles susceptible to be delayed.

Table 12.1.2.1.4 Length of dosing delay.

		Treatment-related		Non-treatment-related		Total	
Length of delay	Median (range)	N	%	N	%	N	%
Length of delay		N	%	N	%	N	%
≤ 7 days		X	X.X				
>7 days and ≤14 days							
> 14 days							

(*) Denominator= Number of cycles susceptible to be delayed.

Listing 12.1.2.1.5 Cycle delays due to AEs

Patient id.	Cycle	Delay reason according to Exposure form	Preferred term code	Adverse event reported (verbatim)	Grade	Relationship	Onset date	Resolved date	Significant consequences

AEs with action = 'Dose delayed' or 'Reduced and delayed'.

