12.1.3 Dose omissions

Listing 12.1.3.1 Dose omissions

Patient id.	Cycle	Day	Cycle start date	Reason for dose omission	Dose omission Spec.

Table 12.1.3.2 Number of patients and cycles with dose omitted, any relationship

	N	%
No. of patients treated	X	X.X
No. of patients susceptible to have a dose omission *		
No. of patients with any dose omitted **		
No. of patients with **:		
No plitidepsin omissions		
1 cycle with plitidepsin dose omitted		
2 cycles with plitidepsin dose omitted		
≥ 3 cycles with plitidepsin dose omitted		
No. of cycles administered		
No. of cycles susceptible to have any dose omitted***		
No. of cycles with plitidepsin dosing omitted****		
No. of cycles with plitidepsin dosing omitted (treatment-related)		

(*) All patients with more than one infusion. (**) Denominator = Number of patients susceptible to have a dose omission

(***) All cycles excluding first cycle. (****) Denominator= Number of cycles susceptible to have a dose omission

NA: Not applicable

Table 12.1.3.3 Number of cycles with treatment-related dose omission by patient

	N	%
No. of patients with:	X	X.X
No omission		
1 cycle with treatment-related plitidepsin dose omitted		
2 cycles with treatment-related plitidepsin dose omitted		
≥ 3 cycles with treatment-related plitidepsin dose omitted		

Denominator= Number of patients that were on treatment on day 8 of cycle 1.

NA: Not applicable

Table 12.1.3.4 Reasons for dose omissions

Reasons for omissions	N	%
Treatment-related	X	X.X
Non-treatment-related		

NA: Not applicable

Listing 12.1.3.5 Dose omissions due to AEs

Patient id.	Cycle	Preferred term code	Adverse event reported (verbatim)	Grade	Relationship	Onset date	Resolved date	Significant consequences

AEs with action = ‘Dose skipped’ on day 8 or 15.

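### As worded, the SAP's delay formula understates Day 1 delays by 14 or 7 days after a Day 15 or Day 8 dose, and the omission and reduction tables use denominators that do not fit or conflict

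*SAP*

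**What the plan says.** **Delays.** SAP 8.2 lets the CRF delay item decide which cycles count as delayed and then sets the length: "For cycles considered as delayed by the investigator, the delay will be calculated as" "Date of current drug administration – Date of previous drug administration – 28". The calculation concerns the Day 1 infusion. Protocol 7.2 gives plitidepsin "on Day 1, 8 and 15 every four weeks (q4wk). A 1-day window is allowed for plitidepsin administration", and the notes to the protocol's Schedule of Assessments equate Day 29 with Day 1 of the next cycle. Listing 12.1.2.1.1 prints the calculated delay beside both cycle start dates, one column being "Previous cycle start date". Table 12.1.2.1.4 groups lengths as up to 7 days, ">7 days and ≤14 days", and more than 14 days.

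**Omissions.** Protocol 7.4 provides for omitting Day 8 or Day 15 infusions in any cycle, and names Cycle 1 explicitly. SAP 8.2 removes only the first infusion of Cycle 1 from delay and modification calculations. Table 12.1.3.2 nevertheless defines the cycles at risk, and the divisor, as "All cycles excluding first cycle. () Denominator= Number of cycles susceptible to have a dose omission". Its patient denominator is "All patients with more than one infusion". The footnote to Table 12.1.3.3 instead reads "Denominator= Number of patients that were on treatment on day 8 of cycle 1".

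**Reductions.** In SAP 12.1.4, the row of Table 12.1.4.2 for cycles at risk of a reduction drops only the first cycle of patients who had a single infusion. The percentage footnotes of Tables 12.1.4.2 and 12.1.4.3 divide by the cycles at risk of an omission.

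**The concern.** The constant 28 is the distance between two consecutive Day 1 infusions. It is not the distance from a Day 8 or Day 15 infusion to the next Day 1. A programmer who follows the only stated formula would obtain delays that are too short, often zero or negative, for cycles that the investigator has marked as delayed.

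Leaving out Cycle 1 is correct in the delay tables, because Cycle 1 cannot be delayed. It does not fit omissions, which can occur in Cycle 1. If Cycle 1 omissions stay in the numerator, the cycle-level rate is inflated; if they are dropped, the rate ignores them. For reductions, the table gives two different bases for one percentage.

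Dose reductions, skipped doses and delays belong to the treatment-safety secondary endpoint (SAP 3.3 and 6.1.2). At stake are the median, range and length rows of Table 12.1.2.1.4 and the cycle-level omission and reduction percentages. Neither ORR nor the futility rules use these tables.

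**Working it through.** **Check of the schedule.** The one numerical result in SAP 8.2 is the intended dose intensity. Three doses of 3.2 mg/m² over four weeks give 3 × 3.2 / 4 = 2.4 mg/m²/wk, as stated. The SAP therefore assumes the same Day 1/8/15 schedule in 28-day cycles.

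**Delay length.** Take the previous cycle's actual Day 1 as time 0. Day 8 is then at 7, Day 15 at 14, and the next Day 1 is due at 28. With a true delay of d days it is given at 28 + d. The formula returns:

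- after a Day 15 dose: (28 + d) − 14 − 28 = d − 14
- after a Day 8 dose (Day 15 omitted): (28 + d) − 7 − 28 = d − 7
- after Day 1 only (Days 8 and 15 omitted): (28 + d) − 0 − 28 = d

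| True delay (days) | Last dose Day 15 | Last dose Day 8 | Last dose Day 1 |
|---|---|---|---|
| 7 | −7 | 0 | 7 |
| 10 | −4 | 3 | 10 |
| 14 | 0 | 7 | 14 |
| 21 | 7 | 14 | 21 |

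After a Day 15 or Day 8 dose, every true delay of 8 to 14 days falls in the row for 7 days or less. After a Day 15 dose, the row for more than 14 days needs d − 14 > 14, a true delay of at least 29 days. A start-to-start calculation gives (28 + d) − 0 − 28 = d in all cases.

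**Effect of the 1-day window.** Let the last dose fall w = −1, 0 or +1 days from its nominal distance to the actual Day 1. The results become d − 14 − w and d − 7 − w, so the understatement is 13 to 15 or 6 to 8 days. For d = 8 to 14 there are 7 × 3 × 2 = 42 combinations. Of these, 41 still give 7 or less. The exception is d = 14 after a Day 8 dose given one day early: 42 − 6 − 28 = 8.

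**Omissions.** No omission rate is assumed. Cycle 1 is 1/k of the cycles of a patient treated for k cycles:

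- k = 1: 100%
- k = 3: 33.3%
- k = 6: 16.7%

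This is the share of cycles left out of the denominator, not a bias in a reported rate. As an illustration, a patient with an omission in each of three cycles contributes 3 to the numerator and 2 to the denominator if Cycle 1 omissions are counted. The patient denominators can also disagree. A patient given only Cycle 1 Day 1, with Days 8 and 15 omitted, has two omissions but is in neither denominator of Table 12.1.3.2, yet is on treatment on Day 8 for Table 12.1.3.3.

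**Reductions.** A patient with k cycles (k of 2 or more) contributes k cycles under the row definition and k − 1 under the footnote. The same count of reduced cycles therefore reads k/(k − 1) times as high under the footnote:

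- k = 3: 3/2 = 1.5
- k = 6: 6/5 = 1.2

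**The case against.** The best defence is that start-to-start was plainly meant. The sentence before the formula refers to the Day 1 infusion, Protocol 7.4 restricts cycle delay to the first infusion of a new cycle, 28 fits only a start-to-start gap, and the delay listing prints both start dates. A result of −7 beside those dates would probably be noticed. This is fair, and start-to-start was probably the intention. It does not make the stated formula correct: the formula and the listing point to different dates, and nothing says which governs.

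The window count depends on the anchor. If doses are timed from planned dates, and Day 1 is a day late while the later dose is a day early, the spacing is 12 or 5 days. A true 13-day delay after a Day 8 dose would then compute as 13 − 5 = 8, a further exception. The 41 of 42 therefore holds for the anchor stated above and describes possible cases, not their frequency. The nominal-day result does not depend on it.

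The denominator faults look like footnotes carried over from neighbouring tables. That is likely, but a carried-over footnote still yields an unsuitable or contradictory percentage if programmed as written. For reductions, Protocol 7.5 bases dose adjustments on toxicity in the previous cycle, so a denominator without Cycle 1 could be defended. The fault is that the row and the footnotes disagree.

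The practical effect is also limited. The number of delayed cycles comes from the CRF item, and Listings 12.1.3.1 and 12.1.3.5 still show Cycle 1 omissions. So do the patient-level rows, in Table 12.1.3.2 for patients with more than one infusion. That is why the point is minor.

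**Conclusion.** The concern holds on all three parts and is minor. On nominal dosing days, the formula read literally understates a Day 1 delay by exactly 14 days after a Day 15 dose and 7 days after a Day 8 dose; it is right only when both were omitted. The omission table excludes a cycle in which the protocol provides for omissions. The reduction percentages have two possible denominators, one cycle per patient apart for patients with at least two cycles. The ratios of 1.5 and 1.2 are for patients with three and six cycles; the documents do not give the cycle counts to be expected. ORR, the futility rules, the adverse event tables, the dose-intensity formula and the number of delayed cycles are unaffected.

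**What to change.** 1. **SAP 8.2.** For cycles flagged as delayed, define delay as the Day 1 date of the current cycle minus the Day 1 date of the previous cycle minus 28. This agrees with Listing 12.1.2.1.1. Keep the CRF flag as the gate: under Protocol 7.4, resuming treatment after the radiological assessment is not a cycle delay.
2. **Tables 12.1.3.2 and 12.1.3.3.** Define susceptible cycles as all cycles, Cycle 1 included, in which a Day 8 or Day 15 infusion was due. Use one patient denominator in both tables: patients for whom Cycle 1 Day 8 was due. State how an infusion is judged to be due, for example recorded either as given or as omitted.
3. **Tables 12.1.4.2 and 12.1.4.3.** Choose one set of cycles susceptible to a reduction, with or without Cycle 1, label it as such, and use it in the row and in both footnotes. Make this change together with item 2; otherwise correcting the omission denominator would also change the reduction percentages.

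The cost is a few wording edits to the SAP text, table rows and footnotes. Cycle start dates and omissions by cycle and day already appear in Listings 12.1.2.1.1 and 12.1.3.1, so these edits need no new data.
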